**unless local guidelines (e.g., Yale University, VACT, the state of CT) require it at the time of study participation.**

After the test day is completed, subjects will be asked to remain on the Biostudies Unit to make sure that there are no after effects of the alcohol or ALLO. A physician will examine them before they are permitted to go home. After the test day, subjects will be encouraged to make arrangements to be driven home. If they are driving themselves home, they will not be permitted to leave until their breathalyzer is at or below ( $\leq$ ) 0.02 and prior to discharge a physician will evaluate them to detect any signs of intoxication that would impair driving ability.

**Blood Draw:** In addition to collecting ALLO, we will also be collecting Ghrelin and Neuropeptide Y (NPY). Recent evidence suggests that peptides such as Ghrelin and NPY may play a role in stress, alcohol craving, and reward; however, this research is in its early stages. The role of these peptides in alcohol consumption and in alcohol use disorders is not well understood. Current evidence from both animal and human research demonstrates that the peptide Ghrelin is strongly and positively related to craving for alcohol. The role of NPY in relation to craving for alcohol is less understood. This project will attempt to understand the role of Ghrelin and NPY in drinking, stress, and craving in heavy drinkers. We will collect Ghrelin and NPY on a total of N=60 completers.

**Follow-up:** After the test day, participants will be contacted for 2 telephone follow-ups. The first telephone interview will be approximately 1 business day after the participant completes their lab session. They will be asked about how they have been doing since their last test day as well as about any alcohol, tobacco, or drugs they may have consumed. The questionnaire will take about 10 minutes to complete. The week 4 follow-up will also be over the phone and will last about 30-60 minutes, where they will be asked about how they have been doing since the test day and will complete a TLFB for the past 4 weeks as well as other surveys outlined in Table 1.

#### **D. Data analysis and sample size considerations:**

Study data will be collected and managed using REDCap electronic data capture tools hosted at VA CT Healthcare System. REDCap (Research Electronic Data Capture) is a secure, web-based application designed to support data capture for research studies, providing 1) an intuitive interface for validated data entry; 2) audit trails for tracking data manipulation and export procedures; 3) automated export procedures for seamless data downloads to common statistical packages; and 4) procedures for importing data from external sources (Harris et al 2009).

**Data Analysis:** Descriptive statistics will be calculated and normality assumptions will be checked prior to analyses. Transformations or non-parametric methods will be used if normality assumptions are not satisfied. The primary analyses will use linear mixed models (LMMs). LMMs are flexible in modeling the variance-covariance structure of the repeated measures, use all available data on an individual, and provide unbiased and efficient results when data are missing at random. Based on Schwartz Bayesian information criterion (BIC) (smaller is better), we will select the appropriate correlation structure for each dependent variable. Medication will be entered as a categorical variable with two levels (placebo, ALLO 100 nM). Stress/Neutral cues will be entered as a within-subject variable with two levels: stress and neutral. Time will also be a within-subject factor (before cue presentation, and 2 times after each cue presentation). **Specific Primary Aims** will examine the effect of medication on craving (assessed with AUQ), and anxiety (assessed with STAI-6) under stress vs. neutral condition, and stimulant/sedative effects of 40 mg% alcohol. We will consider a significant interaction between medication and stress condition with smaller differences between the stress and neutral conditions on active drug (ALLO) supportive of our hypothesis. **Specific Secondary Aims** will examine the effect of medication, under stress vs. neutral, and in combination with alcohol on

subjective mood effects, cognitive functioning and motor coordination. As stated in the specific primary aims, a significant interaction between medication and stress condition with smaller differences between the stress and neutral conditions on active drug (ALLO) vs. placebo will be considered supportive of our hypothesis. **Exploratory Aims** will examine the gender-specific effects by adding gender as a between-subject factor in the models above and testing all possible interactions involving gender. All statistical testing for the primary hypotheses will be two-sided at 0.05 significance level. Post-hoc tests and analyses of secondary outcome measures will be adjusted for multiplicity using the Bonferroni correction.

**Sample size considerations:** With 30 subjects per treatment group, we have at least 80% power to detect large effects ( $f=0.5$ ) for the interactions of interest for Aims 1a, 1b, and 1c assuming alpha=0.05. We can also detect large effects for the comparisons of ALLO dose to placebo ( $d= 0.74$ ) under the same assumptions. The effects we are proposing are based on data from Timby et al. 2006 and van Broekhoven et al 2007 who reported that ALLO administration had a large effect ( $d>0.8$ ) on saccadic eye movement and sedation among healthy subjects.

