- The following assessments will NOT be conducted remotely: physical exam, blood pressure/pulse, blood work, urine toxicology, pregnancy test, and EKG.

**Randomization:** Stratified block randomization will be used to balance treatment assignments within each gender. Our group has used this procedure with repeated success in previous and ongoing studies. The Research Pharmacy will create the randomization tables.

**Script Development:** Two scripts will be developed based on a procedure developed by Lang et al [79-81] and using Scene Construction Questionnaires [81-83]. The questionnaires elicit details on the event and individuals involved, including physical sensations, thoughts, emotions, and cues related to the event described. The stress related scripts will be based on the “most stressful” recent experience. Only stressful experiences rated 8 and above will be used for script development. Stressful experiences related to substance use will not be considered. The neutral script will be based on previously developed neutral scripts that will consist of a relaxed beach scene commonly experienced by most individuals but personalized for each participant. The script development can also be done virtually.

**Alcohol Clamp Procedure:** In this study, we will be using a modified alcohol-IV clamp procedure developed and standardized by Subramanian and colleagues [84], that has been used previously and in ongoing studies by the Co-PI [59]. We will use the latest state-of-the art infusion method CAIS that uses a computerized control of the alcohol infusion that includes real-time pharmacokinetic modeling to optimize the reliability and standardization of the procedure [85]. The infusion will be performed using a 6% ethanol solution in 0.9% saline. The computer assisted administration program automatically calculates and corrects the infusion rate based on real-time BrAc data entry by staff, based on the pharmacokinetic profile of each subject.

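### For Aims 1a and 1b, BIC alone chooses the correlation structure, so the subject-by-cue variance that forms the error term of the primary medication-by-cue test is not guaranteed to stay in the model

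*Combined protocol and SAP*

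**What the plan says.** All of this stands in Section 5, part D, unless noted.

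- Covariance: with the smallest BIC as the criterion, "we will select the appropriate correlation structure for each dependent variable". This is the only rule given.
- Layout: "Stress/Neutral cues will be entered as a within-subject variable with two levels: stress and neutral". For time: "Time will also be a within-subject factor (before cue presentation, and 2 times after each cue presentation". That makes 2 cues x 3 times = 6 ratings per person.
- Primary test for craving (AUQ) and anxiety (STAI-6): "We will consider a significant interaction between medication and stress condition with smaller differences between the stress and neutral conditions on active drug (ALLO" as support for the hypothesis.
- Level: "All statistical testing for the primary hypotheses will be two-sided at 0.05 significance level".
- Allocation (Randomization paragraph, part C): "Stratified block randomization will be used to balance treatment assignments within each gender". Gender enters the models only for the exploratory aims.

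The plan declares linear mixed models but names no random effects, no candidate covariance structures, no degrees-of-freedom method and no robust standard error. No other section supplies them.

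**The concern.** Drug is assigned between people and cue varies within people. The medication-by-cue test asks whether the average stress-minus-neutral difference is the same in the two arms. Its uncertainty comes mainly from how much that difference varies from person to person. The documents give reason to expect such variation. Stress scripts are built on each person's own event, the background section describes people who differ in laboratory stress reactivity, and the ratings come in two separate blocks.

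A structure such as compound symmetry has no term for this variation. It spreads it over the pooled within-person residual and treats that residual as having about 290 degrees of freedom instead of 58. The interaction is then tested against too small an error, and the nominal 0.05 is not held. Because the choice is made separately for each outcome, craving and anxiety could also be tested on different footings.

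**Working it through.** **Inputs from the documents.** 30 per arm, 2 cues, 3 times per cue, two-sided alpha 0.05, detectable d = 0.74, interaction effect f = 0.5.

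**Inputs assumed.** The documents give no variance components. Let r be the subject-by-cue variance divided by the residual variance; the range 0 to 1 is examined. The candidate list is also assumed, in two versions.

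**1. The plan's own figure.** Noncentrality is 0.74 x sqrt(30/2) = 2.866. On 58 df the power is 80.5%, so the stated 80% reproduces. For f = 0.5, noncentrality is 0.25 x 60 = 15. Power on 1 and 58 df is 96.8%, so the claim of at least 80% is true.

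**2. Error terms.** Take the residual variance as 1.

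- Correct error for medication by cue: 1 + 3r, on 58 df.
- Compound symmetry pools 58 df of (1 + 3r) with 232 df of 1: [58(1 + 3r) + 232]/290 = 1 + 0.6r, on 290 df.
- Ratio of standard errors: sqrt[(1 + 0.6r)/(1 + 3r)].
- Type I error if the term is dropped, by normal approximation: 2 x [1 - Phi(1.96 x ratio)].

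| r | 1 + 0.6r | 1 + 3r | SE ratio | Type I error, compound symmetry always used |
|---|---|---|---|---|
| 0.1 | 1.06 | 1.30 | 0.90 | 7.7% |
| 0.25 | 1.15 | 1.75 | 0.81 | 11.2% |
| 0.5 | 1.30 | 2.50 | 0.72 | 15.8% |
| 1 | 1.60 | 4.00 | 0.63 | 21.5% |

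These figures apply when the term is always left out. They are not the behaviour of the BIC rule, which comes next.

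**3. BIC with a subject-by-cue structure among the candidates.** The extra term costs one parameter, a penalty of ln 60 = 4.09 (or ln 360 = 5.89 if observations are counted). In 400,000 simulated trials per value of r with the ln 60 penalty, BIC dropped the term in 77%, 39%, 24% and 1% of trials at r = 0.1, 0.2, 0.25 and 0.5. Overall type I error peaked near r = 0.15, at 6.6% (7.3% with ln 360), and was back to about 5% by r = 0.5.

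**4. BIC with only compound symmetry, AR(1) and unstructured.** The unstructured matrix has 21 parameters against 2, a penalty of 19 x 4.09 = 77.8. BIC therefore rarely reaches it with 60 people. With 1,500 trials per case (simulation error about 0.7 percentage points), the subject variance set at twice the residual variance and no autocorrelation:

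| r | Type I error | Compound symmetry chosen | Unstructured chosen |
|---|---|---|---|
| 0.1 | 8.2% | 100% | 0% |
| 0.25 | 10.6% | 99.4% | 0% |
| 0.5 | 13.0% | 87.9% | 0.1% |
| 1 | 8.4% | 24.3% | 11.4% |

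A separate simulation (4,000 trials per case; total variance 1, subject variance 0.5) gave 8.1%, 11.4%, 13.1% and 12.3% at subject-by-cue variance 0.05, 0.10, 0.15 and 0.20. Since the residual is 0.5 minus that variance, these are r = 0.11, 0.25, 0.43 and 0.67.

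**5. Same three candidates, ratings within a cue also autocorrelated at 0.4.** BIC mostly chose AR(1). Type I error was 5.1% and 5.0% at r = 0.25 and 0.5, with mean SE ratios of 1.05 and 1.02. The separate simulation gave 5-7%.

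**6. Term always kept.** Type I error is 5.0% at every r from 0 to 1.

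**Sensitivity.** Table 2 lists AUQ and STAI-6 at 0, +15, +20 and +25 minutes for the first cue, which is three post-cue ratings where part D counts two. With four times per cue the SE ratio is sqrt[(1 + 4r/7)/(1 + 4r)]. Leaving the term out then gives 13.8% at r = 0.25 and 19.9% at r = 0.5.

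**The case against.** BIC selection of a covariance structure is common practice. The rule is stated in advance and does not look at the treatment p-value. The plan already names cue and time as separate within-subject factors, so an analyst could well include a subject-by-cue effect or a cue-by-time product structure among the candidates. BIC then keeps the term when it is large, and the inflation is modest. Post-cue ratings are only 5 minutes apart, so autocorrelation within a cue is plausible, and that shrinks the problem further. This is a Phase I laboratory study, and Aim 1c has no stress/neutral contrast at all.

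All of that stands as a limit on size and scope. It does not fill the gap, because whether the test runs at 5% or 13% depends on a candidate list that the plan does not give.

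Three stronger readings are tempting and are not supported:

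- That the primary tests will run at 8-13%, or above 20%. The first range needs a restricted candidate list, the second needs compound symmetry to be used whatever BIC says, and the documents state neither.
- That the standard error is always too small. In the autocorrelated case it was on average slightly too large.
- That leaving gender out of the primary model adds to this fault. Gender is constant within a person, so its main effect cancels from the stress-minus-neutral contrast.

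**Conclusion.** This is a specification gap in the primary analysis of Aims 1a and 1b, not an arithmetic error. The plan does not guarantee the variance term that the medication-by-cue test needs. If that variance is real and the selected structure omits it, the test is anticonservative.

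The size rests on assumed variance components and an assumed candidate list. It is a peak of about 6.6-7.3% with a subject-by-cue candidate, up to about 8-13% with only compound symmetry, AR(1) and unstructured, and about 5-7% with those three when within-cue autocorrelation is about 0.4. The direction is clear, the size is uncertain and the remedy is nearly free, so the text should be changed before the data are analysed.

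**What to change.** For Aims 1a and 1b, state in advance that a random subject effect and a random subject-by-cue effect (or an equivalent block structure) stay in the model whatever the BIC. Name Kenward-Roger degrees of freedom. Restrict BIC to the residual correlation across times within a cue, and list the candidates. State how many ratings per cue enter the model, so that part D and Table 2 agree.

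A per-person stress-minus-neutral difference compared between arms is an acceptable alternative. It is equivalent only if it averages over the same time points as the model's medication-by-cue term, which under part D includes the pre-cue rating. A post-cue-only difference is a different contrast and would have to be declared as such.

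Separately, gender is the randomisation stratum and can be included in the primary models at no cost. Its main effect matters for between-group comparisons such as Aim 1c and leaves the medication-by-cue contrast unchanged.

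The cost is a few lines of analysis text, with no new data and no burden on participants. The standard error becomes slightly larger, and correct. The stated power survives, since d = 0.74 with 30 per arm gives 80.5% on the same 58 df, with d read on the per-person contrast.

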***The goal of this Phase I study is to determine whether intravenous infusion of ALLO attenuates (1) stress-induced alcohol craving, stress-induced anxiety and (2) subjective stimulant/sedative effects of alcohol in individuals with AUD using a laboratory paradigm.*** The secondary objective of this project is to characterize the behavioral effects of ALLO in AUD. We propose a double-blind, randomized, between subject, placebo-controlled study in 60 individuals with AUD to compare *one dose (1.5 mg/ml solution) of continuous (200 min.) infusion of ALLO* (targeted plasma of 100 nM [IV bolus of 191 mcg/kg over 60 min. followed by continuous infusion of 57.4 mcg/kg/hr x 140 min.] n=30) to *placebo* (n=30). On a single test day, after 60 min of infusion - when ALLO levels stabilize - stress and neutral cues consisting of personalized 5 min. scripts will be presented in random order. The use of personalized scripts has been shown to produce robust and reliable craving and anxiety in subjects including heavy drinkers[1], alcohol dependent individuals (see the preliminary data section)[2] both with and without psychiatric comorbidity (including work by our group)[3-5] and, in those with other substance use disorders [6]. All participants will also receive alcohol administered intravenously using a clamp procedure, targeting a breath alcohol concentration (BrAc) of 40mg% (40 mg/dL). Alcohol will be administered following script presentation (20 min to target and clamped for

additional 30min). The main outcomes are measures of stress-induced alcohol craving, stress-induced anxiety, and subjective alcohol effects; other secondary outcomes include subjective mood effects, cognitive performance, and motor coordination.

**Hypothesis 1 (Specific Aim 1):** To determine if ALLO (targeted plasma of 100 nM), compared to placebo:

**Aim #1a:** attenuates stress-induced craving for alcohol, measured by the Alcohol Urge Questionnaire (AUQ).

**Aim #1b:** attenuates stress-induced anxiety, measured by the State Trait Anxiety Inventory (STAI-6).

**Aim #1c:** attenuates the subjective stimulant/sedative alcohol effects (target BrAC=40 mg%), measured by the Biphasic Alcohol Effects Scale (BAES).

**Hypothesis 2 (Specific Aim 2):** To characterize ALLO's behavioral effects:

**Aim #2:** to describe ALLO's subjective mood effects, we will use Differential Emotions Scale (DES-R), the Addiction Research Center Inventory (ARCI) and the Similarity to Drugs of Abuse Scale (SDAS).

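### The medication-by-cue success rule cannot be run on the six instruments named for Aims 2 and 3, and primary Aim 1c (BAES) lacks a reference rating and a subscale rule

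*Combined protocol and SAP*

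**What the plan says.** Section 5, part D (Data Analysis) sets up linear mixed models with medication as a two-level factor and cue (stress, neutral) as a two-level within-subject factor. The only time factor is this: "Time will also be a within-subject factor (before cue presentation, and 2 times after each cue presentation").

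The primary aims cover craving and anxiety under stress versus neutral, "and stimulant/sedative effects of 40 mg% alcohol". The criterion for support is a medication-by-cue interaction. The secondary aims "will examine the effect of medication, under stress vs. neutral, and in combination with alcohol on" mood, cognition and motor coordination, and the same criterion is carried over: "As stated in the specific primary aims, a significant interaction between medication and stress condition with smaller differences between the stress and neutral conditions" on ALLO than on placebo.

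Section 2 names DES-R, ARCI and SDAS for Aim 2, HVLT-R and Go/No-Go for Aim 3a, and Grooved Pegboard for Aim 3b. Aim 1c is that ALLO "attenuates the subjective stimulant/sedative alcohol effects (target BrAC=40 mg%), measured by the Biphasic Alcohol Effects Scale (BAES").

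On error control: "All statistical testing for the primary hypotheses will be two-sided at 0.05 significance level", and "Post-hoc tests and analyses of secondary outcome measures will be adjusted for multiplicity using the Bonferroni correction". The sample size paragraph claims at least 80% power "for the interactions of interest for Aims 1a, 1b, and 1c assuming alpha=0.05", and separately for ALLO-placebo comparisons at d=0.74.

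Table 2 (section 6) gives the rating times.

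**The concern.** A within-subject stress-minus-neutral difference needs one rating after the stress cue and one after the neutral cue in the same person. If an instrument is not given in both cue blocks, the interaction named as its success rule does not exist in the data.

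For Aims 2 and 3 the stake is a stated rule that fails and would have to be replaced during analysis. For Aim 1c the stake is larger, because it is one of three primary aims. BAES is a measure of the alcohol phase, so the cue interaction and cue-based time factor do not apply to it, and no other contrast is written down. The reference rating and the deciding subscale could then be chosen after the data are seen. Section 6.1 lists sedation and alcohol-like intoxication among ALLO's common effects, so a change score that starts before the infusion mixes those effects with any change in the response to alcohol.

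**Working it through.** **Step 1. Schedule, from Table 2.**

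| Instrument (aim) | Baseline | -40 | Cue block 1 (0 to +25) | Cue block 2 (+30 to +55) | +90 | +150 |
|---|---|---|---|---|---|---|
| AUQ (1a) | yes | yes | yes | yes | no | no |
| STAI-6 (1b), VAS | yes | yes | yes | yes | yes | yes |
| BAES (1c) | yes | yes | no | +55 only | yes | yes |
| DES-R (2) | yes | yes | no | +55 only | no | no |
| ARCI, SDAS (2) | yes | yes | no | +55 only | yes | yes |
| HVLT-R, Go/No-Go, Pegboard (3) | yes | yes | no | no | yes | yes |

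Instruments named for Aims 2 and 3 that are rated after each cue: 0 of 6. BAES is not rated after each cue either. The Overview in section 5 agrees: it places the mood, cognitive and motor measures in the first hour of infusion, before the cues.

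**Step 2. The plan's own power figure.** Two-sample noncentral t, 30 per arm, 58 df, two-sided 0.05. The noncentrality is 0.74 x sqrt(30/2) = 2.866 and the critical t is 2.002, so power is 80.5%. The d=0.74 statement reproduces. Reading f=0.5 as a two-group contrast (d = 2f = 1.0) gives 96.8%, so at least 80% is true as well. The arithmetic is sound. What is missing for Aim 1c is the contrast to which it applies.

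**Step 3. Why the reference rating matters: sedation (illustration).** Assume additive effects, a true attenuation of alcohol's sedative effect of 0.74 raw SD, and an ALLO own effect s that raises BAES sedation. The value of s and the correlation r between the two ratings are not in the documents. For change from pre-infusion Baseline, the standardized difference in the attenuation direction is (0.74 - s) / sqrt(2(1 - r)). At r = 0.5 the divisor is 1. Chance of a significant result in that direction:

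| Own effect s (SD) | 0 | 0.2 | 0.4 | 0.6 | 0.8 |
|---|---|---|---|---|---|
| r = 0.3 | 66% | 41% | 19% | 7% | 1.6% |
| r = 0.5 | 80% | 54% | 25% | 8% | 1.4% |
| r = 0.7 | 95% | 76% | 39% | 10% | 1.2% |

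At s = 0.8 and r = 0.5 the net difference is 0.74 - 0.8 = -0.06 SD, slightly in the wrong direction.

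**Step 4. Stimulant (illustration).** If ALLO alone lowers BAES stimulant by 0.2 or 0.4 SD and leaves the alcohol response unchanged, apparent support arises with probability 12% or 33% at r = 0.5, against a nominal 2.5% in that direction.

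**Step 5. Two subscales.** If a result on either subscale at 0.05 counted as success, the false-positive chance would be 1 - 0.95 x 0.95 = 9.75% for independent subscales, and about 9.1% at an assumed correlation of 0.5. At 0.025 each, power at 0.74 is 71.3%, and the effect detectable with 80% power rises from 0.74 to 0.81.

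**The case against.** Several points on the other side are fair.

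- **Aims 2 and 3 are descriptive.** Section 2 words them that way and no data are lost. This stands: that part is a rule correction. A reader might infer that these aims cannot be analysed, but arm differences are available at every scheduled rating. Nor are the instruments unrated once both cues have been given: each of the six has at least one such rating (+55, or +90 and +150). What is missing is a rating after each cue.
- **VAS items touch on mood and are rated in both cue blocks.** True, but VAS is not among the instruments named for Aim 2.
- **Random cue order allows a between-subject comparison at +55.** It does for DES-R, ARCI and SDAS. That is a different contrast, which the plan does not describe, with about 15 per cell.
- **Medication by time is obvious for BAES.** Largely so. The sample size paragraph lists the 1c interaction apart from the ALLO-placebo comparison, so a reader who infers that Aim 1c might be a plain arm comparison with no reference goes beyond the text. Aim 1c also names target BrAC, which points to +90. But medication by time still needs a starting rating, and Baseline, -40 and +55 all remain open.
- **The percentages are assumed.** They are. The d>0.8 for sedation in the sample size paragraph comes from healthy subjects, and nothing shows that it carries over to BAES in AUD. The 1.4% is the end of a range and not a forecast. The plan does not adopt an either-subscale rule, so 9-10% is not its planned error rate.

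**Conclusion.** Two conclusions hold.

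First, the medication-by-cue success rule cannot be run on any of the six instruments named for Aims 2 and 3. This follows from Table 2 alone and needs no assumption. It does not touch AUQ, STAI-6 or VAS.

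Second, primary Aim 1c has no stated reference rating and no rule for its two subscales, although an interaction is powered for it. Steps 3 and 4 show the direction of the risk: starting from pre-infusion Baseline can hide attenuation on sedation and imitate it on stimulant. The size depends on an own effect and a correlation that the documents do not give, and on additivity.

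The first part is a correction of wording. The second should be settled before unblinding, because the choice can move the answer to a primary aim either way.

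**What to change.** SAP text only; every rating used is already scheduled.

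1. Limit the medication-by-cue rule to AUQ, STAI-6 and VAS.
2. Define Aim 1c as medication by time on BAES from +55 (on infusion, before alcohol) to the rating Table 2 labels as target reached (+90), adjusted for pre-infusion BAES, gender and cue order by time. Add a sensitivity analysis with medication by cue order by time, or split by second cue, because residual stress at +55 may differ by arm in those whose second cue was stress. Report stimulant and sedation separately. Attenuation on a subscale means a smaller alcohol-induced change on ALLO than on placebo. If support on either subscale counts as success, test each at 0.025.
3. For Aims 2 and 3, replace the cue rule with baseline-adjusted ALLO-placebo differences: at -40 for all six instruments, noting that this is 20 minutes into infusion and before levels stabilize; at +55 for DES-R, ARCI and SDAS, adjusted for cue order; and at target BrAC for all except DES-R, which has no rating after alcohol.
4. Reword the power sentence. For Aim 1c the interaction is medication by time, and 30 per arm detects 0.74 SD of the change with 80% power at two-sided 0.05, or 0.81 at 0.025 (0.74 then has 71%). State the unit: 0.74 SD of the change equals 0.74 x sqrt(2(1 - r)) raw SD, which is 0.88, 0.74 or 0.57 at assumed r of 0.3, 0.5 or 0.7.

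Costs: a less favourable power figure if 0.025 is used; a possible ceiling effect when the +55 score is already raised; residual second-cue stress at +55, which the sensitivity analysis probes but does not remove; and only approximate removal of ALLO's own effect, since section 5 expects plasma levels to fluctuate and Table 2 draws no ALLO level between +55 and +150.

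### The primary AUQ and STAI-6 models omit the randomisation stratum (gender) and the randomised cue period: no bias, and a conditional, mostly small loss of precision

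*Combined protocol and SAP*

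**What the plan says.** - **Randomisation** (Research Plan, C. Study Procedures, Randomization): "Stratified block randomization will be used to balance treatment assignments within each gender". The Overview plans 15 men and 15 women per arm.
- **Cue order** (Overview): each participant receives the stress and neutral cues in random order in one session, and the second cue starts once stress has returned to baseline. The method of randomising order, and whether order is balanced by arm, is not stated.
- **Primary models** (D. Data analysis): three terms are named. The arm is the first: "Medication will be entered as a categorical variable with two levels (placebo, ALLO 100 nM". The type of cue is the second, given as follows: "Stress/Neutral cues will be entered as a within-subject variable with two levels: stress and neutral". The third is the rating occasion, described in these words: "Time will also be a within-subject factor (before cue presentation, and 2 times after each cue presentation". That third term is therefore the position within a cue block, not first versus second cue.
- **Primary test for Aims 1a and 1b**: the medication x stress-condition interaction, two-sided at 0.05.
- **Covariance**: by BIC, "we will select the appropriate correlation structure for each dependent variable".
- **Gender**: the exploratory aims "will examine the gender-specific effects by adding gender as a between-subject factor in the models above". No section names a period, order or sequence term.
- **Power** (Sample size considerations): with 30 per arm, at least 80% at f=0.5 "for the interactions of interest for Aims 1a, 1b, and 1c assuming alpha=0.05". A separate statement covers the simple contrast between arms: "We can also detect large effects for the comparisons of ALLO dose to placebo", with d=0.74.

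**The concern.** A factor used to restrict the randomisation normally belongs in the primary model; otherwise the variation it explains stays in the error term although the design has balanced it across arms. Cue order is also randomised, so a different response to whichever cue comes second adds noise to the stress-minus-neutral difference. At stake are some power for Aims 1a and 1b and, depending on the covariance structure chosen, the accuracy of the standard error. The exploratory gender models do not close the gap: they also add gender x medication terms and leave the primary test as it is. If the terms are not fixed in advance, a later covariate choice remains open.

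**Working it through.** **Inputs.** From the documents: 30 per arm, 15 men and 15 women in each, two-sided alpha 0.05, f=0.5 for the interactions, d=0.74 for ALLO versus placebo. Assumed, because the documents give no figure: a gender difference g in the stress-minus-neutral response and a period shift of +/-p, both in units of the residual SD of that difference.

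**1. The plan's own figures.** Noncentral t on 58 df, noncentrality d x sqrt(30/2):
- d=0.74: 80.5%.
- f=0.5 read as d=2f=1.0: 96.8%.

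Both stated claims reproduce. The plan gives no f-to-d conversion, and d=1.0 is the cautious reading. Under the within-between formula (noncentrality f^2 x N x 2/(1-rho)), d is 1.4 at rho=0 and 2.0 at rho=0.5, and any loss is smaller.

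**2. What cancels.** Let D be stress minus neutral for one person. The medication x cue test compares mean D between arms. A gender effect that is the same under both cues drops out of D. What can remain is

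D = delta x arm + g x (gender, +/-0.5) + p x (order, +/-1) + e, SD(e)=1.

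Arm is randomised independently of order and is balanced on gender, so omitting g and p leaves the expected arm difference unchanged. In simulation the bias was at most 0.006 SD.

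**3. Power without the terms.** SD(D) = sqrt(1 + p^2 + g^2/4), and the effective d is d/SD(D):

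| Assumed shift | SD(D) | Power, d=1.0 | Power, d=0.74 |
|---|---|---|---|
| none | 1.000 | 96.8% | 80.5% |
| p=0.25, g=0 | 1.031 | 95.9% | 78.1% |
| p=0.25, g=0.5 | 1.061 | 94.8% | 75.7% |
| p=0.5, g=0 | 1.118 | 92.6% | 71.3% |

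This formula treats gender as unstratified, so it slightly overstates the gender loss.

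**4. Simulation** (40,000 trials per setting), unadjusted versus adjusted for gender x cue and period:
- Both shifts (g=0.5, p=0.25), coin-flip order: 95.5% vs 96.5% at d=1.0; 76.4% vs 79.8% at d=0.74.
- Both shifts, order balanced within arm and gender: 95.8% vs 96.8%; 76.9% vs 80.4%.
- No shifts, coin-flip order: 96.6% vs 96.3%; 80.3% vs 79.7%.
- No shifts, balanced order: 96.9% vs 96.9%; 80.3% vs 80.3%.

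**5. Change from the pre-cue rating.** If the test is on this scale, a constant +/-0.25 shift cancels and adjustment gains nothing (d=0.74: 80.4% unadjusted, 79.6% adjusted). A shift in the post-cue ratings only does not cancel (78.2% vs 79.9%).

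**6. Type I error.**
- With a standard error based on D, which corresponds to a covariance with a subject-by-cue component, the unadjusted test is slightly conservative under a gender x cue effect: 4.2% at g=0.5 and 3.6% at g=0.67 (about 4% in a repeat run).
- Under plain compound symmetry, with six ratings per person and rating residual SD 1, Var(D) without a shift is 2/3. A first-to-second-cue shift s with coin-flip order makes it 2/3 + s^2. The model's residual mean square rises only to 1 + 60 x 6 x (s^2/4)/290, and the model takes 2/3 of that as Var(D).
  - s=0.3: 0.757/0.685 = 1.10, type I error 6.2%.
  - s=0.5: 0.917/0.718 = 1.28, type I error 8.3%.
- Simulation of the same case gave 6.2% and 8.5%. With order balanced within arm it gave 4.8% and 4.3%.

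**The case against.** The strongest case against is that nothing the plan claims is overturned. At f=0.5 the stated power is at least 80%, and every setting examined leaves it above 92%. The larger losses use d=0.74, which the plan gives for ALLO versus placebo and not for the interactions. Every shift size is assumed. The return-to-baseline step limits carry-over, the design already balances gender, and the exploratory models will supply gender-adjusted results. Adjustment can also lose a little power when there is nothing to adjust for. All of this stands. It keeps the point minor and makes d=0.74 a sensitivity case only. It does not remove the omission: the return-to-baseline step does not model a weaker reaction to the second cue, and the exploratory fit does not alter the primary test.

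A reader might infer three stronger things that the documents do not support:
- **That the primary estimate is biased.** Gender is balanced by design and order is randomised, so it is not.
- **That the interactions fall below 80% power.** They do not in any setting examined at the stated effect size.
- **That any gender difference in craving or anxiety harms the test.** Only a gender x cue difference can.

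The opposite claim, that type I error can never be inflated, is also too strong, because BIC may select compound symmetry.

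**Conclusion.** The omission is real and minor. The medication x cue estimate is unbiased. Whether precision is lost depends on a gender x cue difference or a period shift that no section quantifies. The power loss at d=1.0 is about 1 to 2 points with gender x cue 0.5 SD and period +/-0.25 SD together, and about 4 points (96.8% to 92.6%) with period +/-0.5 SD alone. At d=0.74 the corresponding losses are about 4 to 5 and 9 points. Calling the loss small therefore holds for modest shifts, not for every conceivable one.

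Type I error stays at or slightly below 5% provided the covariance has a subject-by-cue component or order is balanced within arm. It reaches about 6% to 8.5% only if BIC selects plain compound symmetry, order is simply randomised, and the period shift is 0.3 to 0.5 rating SD.

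These results are for AUQ and STAI-6. For BAES (Aim 1c) any gain is speculative: a gender main effect would matter if arms were compared on level, but no level comparison is a stated test, and under medication x time only gender x time would matter.

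**What to change.** 1. Prespecify gender and gender x cue as fixed effects in the primary AUQ and STAI-6 models. Keep all gender x medication terms exploratory, as now.
2. Balance cue order within arm and gender on the randomisation list that the Research Pharmacy already prepares, and include period (first or second cue) in these models. Period can be left out if the test is fixed as change from the pre-cue rating and only a constant shift is expected.
3. Limit the structures BIC may choose from to those with a subject-by-cue component.
4. In the BAES model add gender, and gender x time if Aim 1c is tested as medication x time. Cue order is not needed there.

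**Cost.** A few lines of analysis wording, one column on the randomisation list and 2 to 3 degrees of freedom. The gender terms cost essentially nothing (80.2% vs 80.3% at d=0.74 when no effect exists). If there is no period effect, the period term costs under 1 point of power with independent order (0.6 to 0.9 at d=0.74, 0.3 at d=1.0) and about 0.1 or less with balanced order.
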